Withdrawal Criteria	
 • Patients who are eligible for discharge from their cardiac situation but cannot be discharged for other medical reasons will be excluded from the trial • Patients who withdraw their consent will be excluded from the trial • Patients who violate the protocol will be excluded from the trial

3 Study-Design

Studiendesign BIC-8: Copeptin as a rule-out marker in ACS

4 Introduction

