7.1 General Patient Flow

Consecutive N-STEACS patients of the Chest Pain Unit with a negative Troponin T at admission will be invited to participate. Troponin T is tested as part of the standard management of patients with suspected acute coronary syndrome. Patients who give their written informed consent will be randomized into one of two study arms (experimental and standard management).

Experimental Arm: Further management dependent on Copeptin result

1. Patients of the above described characteristics who test **negative for Copeptin** at admission will be considered low-risk. In these patients we abstain from further ACS evaluation and instead discharge them into ambulant care. Before discharge patients will have a final visit to secure their well-being. The visit includes a physical examination, an ECG and an assessment for MACE and bleeding events.

Patients who show any signs and symptoms of an acute illness requiring in-hospital treatment will not be discharged (see withdrawal criteria 5.3). This decision is at the discretion of the attending physician.

To secure the patients safety they will be discharged into each co-operating network of resident cardiologists . Patients are to see a cardiologist within a maximum of 3 days after discharge (if discharge falls on a Friday), preferably on the next day after discharge. Further appointments will be at the discretion of the resident cardiologist (see 7.2).

2. Patients with the above described characteristics who test **positive for Copeptin** at admission will be managed as by standard practice i.e. patients will be evaluated as by standard of care abiding current guidelines for the management of patients with suspected ACS

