8.4 Enrolment and randomization

Patients will be assigned to their study group by randomization via sealed envelopes as soon as the written informed consent has been signed.

The Copeptin test result will not automatically be communicated to the Emergency Department but will need to be requested via telephone after the randomization. It will only be released for patients in the experimental group. To assure this, the randomization letter for patients in the experimental group will contain a code which will be noted down in the central laboratory before releasing the Copeptin value.

The code can be compared with the code in the patient's randomization letter to proof adherence to this process.

In patients who are randomized to the control group, the Copeptin result will only be documented at the laboratory and will not be available to the investigators during the recruitment period.

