8.7 Follow-up

All patients will have a 30-day and a 90-day follow-up. Both follow-ups are telephone visits to assess:

- Survival
- MACE and bleeding complications

In case of death or hospitalization during the study period medical records will be requested. The patient will consent to this in the informed consent form.

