10.1 Premature termination of the individual participant

- Patients who are eligible for discharge from their cardiac situation but cannot be discharged for other medical reasons will be excluded from the trial
- Patients who withdraw their consent will be excluded from the trial
- Patients who violate the protocol will be excluded from the trial

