10.3 Follow-up and continuing treatment after regular / premature termination

All patients who have not been excluded from participation will be contacted via telephone for a 30 day follow-up to assess MACE and bleeding events.

All patients will be contacted via telephone after 90 days to assess MACE and bleeding events. All efforts should be made to contact all patients for the 90 day follow-up telephone visit, if the consent to do so is granted.

11 Assessment of MACE and bleeding events

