14.2 Statistical analysis

14.2.1 Definition of population for analysis

First a check of the success of randomisation will be conducted: Bivariate comparisons of basic demographics and baseline risk-markers between experimental group and control group .

Exact Fisher tests will be conducted for comparison of proportions of the main outcome in case of a successful randomisation. But logistic regression analysis will also be employed to adjust for potential confounding.

If more than 10% of patients are lost during follow-up, additional intention to treat analyses will be conducted.

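### Intention-to-treat analysis is only an extra, run if more than 10% are lost, while patients can be excluded after randomisation; this implies a default comparison that is not as-randomised

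*Protocol*

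**What the plan says.** Section 14.2.1, whose heading promises a definition of the analysis population, gives the primary test: "Exact Fisher tests will be conducted for comparison of proportions of the main outcome in case of a successful randomisation". It does not say in which patients. Its only sentence on an analysis set is: "If more than 10% of patients are lost during follow-up, additional intention to treat analyses will be conducted".

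Patients are randomised at consent (Section 8.4): "Patients will be assigned to their study group by randomization via sealed envelopes as soon as the written informed consent has been signed". The Copeptin result is released, and discharge decided, only afterwards. The synopsis (Withdrawal Criteria) and Section 10.1 then remove some patients: "Patients who violate the protocol will be excluded from the trial", and "Patients who are eligible for discharge from their cardiac situation but cannot be discharged for other medical reasons will be excluded from the trial".

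Section 7.1, in the Copeptin-negative branch of the experimental arm, adds: "Patients who show any signs and symptoms of an acute illness requiring in-hospital treatment will not be discharged (see withdrawal criteria 5.3"), a decision left to the attending physician. The cross-reference is wrong, since Section 5.3 describes the Endpoints Committee; the withdrawal criteria are in the synopsis and Section 10.1.

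On follow-up, Section 8.7 says: "All patients will have a 30-day and a 90-day follow-up". Section 10.3 says: "All patients who have not been excluded from participation will be contacted via telephone for a 30 day follow-up to assess MACE and bleeding events". The same Section 10.3 has all patients called at 90 days.

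**The concern.** The trial is meant to show that early discharge of Copeptin-negative patients does not raise 30-day MACE (Section 5). Finding no excess supports changing practice, so a selection that flatters the experimental arm acts in the dangerous direction.

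Randomisation protects the comparison only if patients stay in the arm to which they were assigned. Here they can be removed after the Copeptin result is known, by staff who know the arm (Section 14.2.3 accepts that treating physicians cannot be blinded to it). One route to removal is tied to a discharge step that Section 7.1 describes for the experimental arm. Those held back as acutely ill are plausibly at higher risk, and MACE includes death from any cause. The one safeguard, an intention-to-treat analysis, depends on an observed loss rate that says nothing about this selection.

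**Working it through.** **Inputs.** 446 patients per arm, 892 in total (synopsis). MACE rates of 6.4% at 6 weeks and 7.8% come from a study cited in Section 14.2.2. They are not stated as design rates, and the endpoint is at 30 days. The exclusion fraction and the MACE rate among excluded patients are my assumptions; the protocol gives neither. The sample size cannot be re-derived, because Section 14.1 refers to appendix 2, which is not shown. Nothing below depends on how it was obtained.

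**The trigger.** 10% of 892 is 0.10 × 892 = 89.2. Up to 89 losses (89/892 = 9.98%) bring no intention-to-treat analysis; 90 (10.09%) do.

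**Selective exclusion.** Let both arms have the same true rate p. Remove a fraction f of the experimental arm with MACE rate r, and nobody from the control arm. The rate in those remaining is

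(446p − 446f·r) / (446 − 446f) = (p − f·r)/(1 − f),

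and the spurious difference, experimental minus control, is −f(r − p)/(1 − f). With r = 20%:

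| True rate p | Excluded f | Patients | Rate in those remaining | Spurious difference |
|---|---|---|---|---|
| 6.4% | 5% | 22.3 | (28.54 − 4.46)/423.7 = 5.7% | −0.7 points |
| 6.4% | 10% | 44.6 | (28.54 − 8.92)/401.4 = 4.9% | −1.5 points |
| 7.8% | 5% | 22.3 | (34.79 − 4.46)/423.7 = 7.2% | −0.6 points |
| 7.8% | 10% | 44.6 | (34.79 − 8.92)/401.4 = 6.4% | −1.4 points |

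Over f from 2% to 10% and r from 10% to 30%, the spurious advantage runs from about 0.04 to 2.6 points.

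**Would the trigger respond?** As worded it refers to patients lost, so exclusions would not count. Even if they did, 44.6 patients are 44.6/892 = 5.0% of the trial, so with no other losses the threshold is still not reached.

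**Can an intention-to-treat analysis use the excluded patients?** Only if their 30-day status is known. Section 8.7 promises follow-up for all; Section 10.3 restricts the 30-day call to those not excluded. Under Section 10.3, even a triggered analysis could lack the primary outcome for the patients it is meant to restore.

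**The case against.** **The default set is never named.** This is true. The conditional sentence could be read as an extra analysis to handle lost patients, added to an as-randomised comparison of available data, and a statistical analysis plan that is not shown might say so. A reader might infer that the protocol states a completers-only primary analysis. It does not; that is an implication of the wording together with the exclusion rules. What stands is that the protocol itself makes intention-to-treat conditional, and nothing in it makes an as-randomised analysis unconditional. A later plan would have to override that rule.

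**Excluded patients might count as lost.** A reader might infer that exclusions can never meet the trigger. Loss to follow-up is not defined, and Section 10.3 leaves room for excluded patients to be counted as lost, so the text is unclear rather than decisive. The illustration holds on either reading, as shown above.

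**Losses below the threshold can exceed all events.** The temptation is to set 89 losses against about 57–70 MACE in the whole trial (892 × 0.064 and 892 × 0.078). That is not a measure of bias: at the same rates, 89 lost patients would carry about 6–7 events (89 × 0.064 = 5.7; 89 × 0.078 = 6.9). Nor does deleting the trigger recover unknown outcomes. That is a missing-data problem and needs its own analysis.

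**Per-protocol has a proper place in a no-worse-than comparison.** It does, because intention-to-treat can dilute a real harm. This is a reason to report both sets. It is no reason to make one of them depend on an observed loss rate.

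**The illustration is one-sided.** Similar exclusions in the control arm would largely cancel. This stands as a limit on the size, though Section 7.1 gives a specific reason to expect asymmetry.

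**Conclusion.** The point holds: as written, the protocol makes an as-randomised analysis an optional extra, while permitting exclusions after randomisation that can differ by arm and may leave the primary outcome uncollected. Under the stated assumptions (equal true rates of 6.4% or 7.8%, 5–10% of the experimental arm excluded, a 20% MACE rate among them, no control-arm exclusions), the Copeptin arm would look about 0.6–1.5 points safer than it is without meeting the trigger. How this compares with any margin cannot be judged from the visible text.

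That the wording makes intention-to-treat conditional, and that Sections 8.7 and 10.3 conflict, is certain. What the default set is remains an inference, and the size and direction of any bias are illustrative. The adjusted logistic regression in Sections 14.2.1 and 14.2.3 does not cure the problem, since it cannot bring back patients who have been removed.

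**What to change.** 1. In Section 14.2.1, delete the 10% trigger. State that all randomised patients are analysed in their assigned arm, unconditionally, with the per-protocol analysis reported beside it and the no-higher-MACE conclusion examined in both.
2. In the synopsis and Section 10.1, separate leaving the study pathway from leaving the study. Patients who violate the protocol or are not discharged, and have not withdrawn consent, stay in the analysis and in follow-up. Correct the cross-reference in Section 7.1.
3. Amend Section 10.3 to agree with Section 8.7, so that these patients also receive the 30-day call.
4. Add a sensitivity analysis for unknown 30-day status over a range of assumed event rates. Counting every missing patient as an event should serve only as an extreme bound. With 44 of 446 lost in each arm and equal observed rates, extreme assignment moves the difference by up to 44/446 = 9.9 points either way.

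The cost is a few sentences of amendment, some additional 30-day calls and slightly more analysis.

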14.2.2 Analysis of endpoint

Safety of discharging patients with negative Troponin and negative Copeptin at baseline We chose a primary safety endpoint to prove that discharge of these patients does not increase their mortality or their risk for cardiac events like survived sudden cardiac arrest, myocardial infarction, re-hospitalisation for acute coronary syndrome, acute unplanned PCI, coronary artery bypass grafting (CABG) and documented life-threatening arrhythmias (VF, VT, AV-block III). [name] et al. saw a 6 week MACE rate of 6.4% in 266 patients with a serial negative Troponin result, who were evaluated for an acute coronary syndrome and a 7.8% MACE rate in all patients who were sent home after judgment of the attending physician.

14.2.3 Methods against Bias

Selection bias should be minimized by inviting ALL consecutive patients in all three centers who fulfill the stringent inclusion / exclusion criteria. A volunteer bias seems unlikely in this context (no completely new highly advertised treatment or similar).

Confounding bias for known and unknown confounders should be minimized by a successful randomization. Additionally, even if the randomization proved to be successful, the main findings (see hypotheses) will in any case be validated by multivariate logistic regression modeling adjusting for all potential confounders (demographics, risk factors and risk markers).

Information bias will be minimized by standardized testing procedures for biomarkers and by training of the involved centers for standardization of management protocols. Blinding cannot be performed on the patient side because the management procedures of the arms tested differ; the same is true for the treating physician. However the major outcomes are "hard" data and it is hard to imagine information bias in the form of measurement bias may occur here. Additionally, any conflict of interest from treating physicians will be excluded.

15 Reporting

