5.1 Primary endpoint

Rate of MACE (all- cause death or survived sudden cardiac arrest, myocardial infarction, re-hospitalisation for acute coronary syndrome, acute unplanned PCI, coronary artery bypass grafting (CABG) and documented life-threatening arrhythmias (VF, VT, AV-block III)) within 30 days Copeptin vs. Control group

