5.3 Endpoints Committee

The Endpoints Committee will be composed of cardiologists and ED physicians. This Committee is responsible for assessing the primary and secondary efficacy endpoints.

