7.5 Standard process

Copeptin results will not be revealed to the treating physicians. Patients will be managed as by standard practice i.e. patients will be evaluated as by standard of care abiding current guidelines for the management of patients with suspected ACS.

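### Section 14.2.3 dismisses measurement bias because outcomes are hard, but the open-label primary MACE includes judgement-based components and nothing listed there protects their classification

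*Protocol*

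**What the plan says.** Five parts of the protocol bear on this point.

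- **Section 14.2.3** concedes the open design: "Blinding cannot be performed on the patient side because the management procedures of the arms tested differ; the same is true for the treating physician". It then calls the major outcomes hard and concludes that "it is hard to imagine information bias in the form of measurement bias may occur here". The measures it offers against information bias are standardised biomarker testing, training of centres in the management protocols, and exclusion of conflicts of interest among treating physicians.
- **Section 5.1**, repeated in 11.1, defines the primary 30-day MACE. Besides death, survived arrest, infarction and documented arrhythmia, it includes "re-hospitalisation for acute coronary syndrome, acute unplanned PCI, coronary artery bypass grafting (CABG").
- **Section 5.3**: "The Endpoints Committee will be composed of cardiologists and ED physicians". Their task: "This Committee is responsible for assessing the primary and secondary efficacy endpoints". The section does not say whether members see the arm or the copeptin value. The protocol lists efficacy endpoints (5.2.1) and safety endpoints (5.2.2) separately.
- **Section 8.4** says that a control patient's copeptin result "will not be available to the investigators during the recruitment period". Section 7.5 adds, with no end date: "Copeptin results will not be revealed to the treating physicians".
- **Sections 8.7 and 8.8** follow every patient by telephone at 30 and 90 days and request medical records after a death or hospitalisation. The synopsis ends recruitment in February 2012 and the study in autumn 2012.

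**The concern.** The argument in 14.2.3 holds for death and largely for a documented arrhythmia. It does not hold for the rest of the composite. Whether a chest-pain readmission is called ACS, whether a PCI counts as acute and unplanned, and whether a troponin movement is called infarction are judgements. Here they are made by clinicians who know the arm and, in the experimental arm, the copeptin value.

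The protocol itself expects knowledge of the result to affect care. Section 9 says that copeptin-positive patients may be treated more intensively, and that patients will be readmitted on any suspicion. The information behind a diagnosis also differs by arm: section 7.1 stops further ACS evaluation in copeptin-negative experimental patients, while controls complete it.

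The claim is that MACE does not increase (sections 5 and 14.2.2). It therefore rests on two event rates being close, and a few events labelled differently in one arm can matter.

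**Working it through.** The point contests no figure of the plan. The sample-size derivation is in appendix 2, which is not shown, so no margin or error rate can be taken from the text.

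**1. Do the listed safeguards reach event classification?** Biomarker standardisation concerns the assay. Training concerns patient management. The conflict-of-interest statement concerns motive. None says who labels an event or with what knowledge. The committee in 5.3 does assess the primary endpoint, but 14.2.3 does not refer to it and 5.3 does not mention masking.

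**2. What does the remit cover, read literally?**

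| Endpoint | Where listed | Within the remit in 5.3? |
|---|---|---|
| 30-day MACE and its components | 5.1 | Yes, as primary endpoint |
| Angiography, PCI or CABG after index angiography | 5.2.1 | Yes, as secondary efficacy |
| 90-day MACE | 5.2.2 | Not named |
| Bleeding | 5.2.2 | Not named |
| Re-hospitalisation for *suspected* ACS | 5.2.2 | Not named; 5.1 counts re-hospitalisation for ACS |

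**3. How many controls are still in follow-up when the stated withholding ends?** Inputs: 446 per arm (synopsis); follow-up of 30 and 90 days (8.7); recruitment of 12 months (synopsis), with 18 months as a longer case because 5.5 estimates a trial duration of 12/18 months. Even accrual is assumed. Share = follow-up days / recruitment days.

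- 12 months, 30 days: 30/365 = 8.2%; 0.0822 × 446 ≈ 37 controls.
- 18 months, 30 days: 30/547.5 = 5.5%; 0.0548 × 446 ≈ 24 controls.
- 12 months, 90 days: 90/365 = 24.7%; 0.2466 × 446 ≈ 110 controls.
- 18 months, 90 days: 90/547.5 = 16.4%; 0.1644 × 446 ≈ 73 controls.

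**4. How far can relabelling move the result?** This is an illustration. The assumed MACE rate is 6.4% to 7%; section 14.2.2 cites 6.4% and 7.8% at six weeks.

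- Events per arm: 446 × 0.064 = 28.5 and 446 × 0.07 = 31.2, so about 29 to 31.
- Relabelling 4 or 5 events in one arm: 4/446 = 0.9 and 5/446 = 1.1 points, so about 1 point.
- Half-width of a 95% interval for the difference, 1.96 × √(2p(1−p)/446): 3.2 points at 6.4% and 3.3 points at 7%. The shift is about a third of that.

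**5. What would that do to a non-inferiority conclusion?** Take a control rate of 6.4%, a true excess equal to an assumed margin *m* of 3 to 5 points, and a one-sided 2.5% test. If 10% of experimental-arm events are lost, that is 0.1 × 446 × 0.094 = 4.2 to 0.1 × 446 × 0.114 = 5.1 events. The observed experimental rate is 0.9 × (0.064 + *m*) and the observed difference is *d*. The error is Φ((*m* − *d*)/SE − 1.96), with SE taken from the observed rates.

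- *m* = 3 points: *d* = 2.06, SE = 1.75, error 7.7%.
- *m* = 5 points: *d* = 3.86, SE = 1.85, error 9.0%.

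So losing 4 to 5 events in one direction would raise a nominal 2.5% error to about 8–9%. Nothing in the protocol says that this many would be lost.

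**The case against.** **The committee's masking may be settled elsewhere.** A reader might infer from 5.3 that the committee is unmasked. The text does not say so. It is silent, and a charter or SAP often settles this. The objection stands: silence alone is no defect. What can be criticised is the positive statement in 14.2.3 that the bias is hardly imaginable.

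**Protections exist.** It would be wrong to say that the protocol has none. A committee assesses the primary endpoint, records are requested for deaths and hospitalisations, and section 11.2 has all MACE and major bleeding documented whatever the suspected cause. These help complete ascertainment. They do not ensure that labelling is independent of the arm.

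**The remit gap is narrower than it looks.** One might read 5.3 as leaving infarction, PCI and arrhythmia unadjudicated. Within 30 days they are components of the primary endpoint and so are covered. Bleeding is also uncertain, because the synopsis lists it directly after the angiography and PCI endpoints.

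**The limit in 8.4 has a small reach.** It concerns investigators and control values only. Treating physicians stay blinded to those values under 7.5 and 5.4, and the text does not say that release follows the end of recruitment. Quoting 8% of all patients would overstate it, because experimental-arm values are released by design. The 37 controls are 37/892 = 4% of the trial and would yield about 37 × 0.07 = 2.6 primary events (24 × 0.064 = 1.5 in the longer case). The arm is known anyway. This part is secondary.

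**Masked review does not reach the decisions.** It cannot change whether a patient was readmitted or had a PCI. This stands, and limits what the fix can achieve.

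**Conclusion.** The point holds in a limited form. The reasoning in 14.2.3 does not fit the composite in 5.1, because several components rest on judgement in an admittedly open trial and the safeguards listed there do not address classification. Two pieces of wording add to this. The remit in 5.3, read literally, omits the safety endpoints outside 30-day MACE. The withholding in 8.4 ends while about 24–37 controls are still within 30 days and 73–110 within 90 days, assuming even accrual over 18 to 12 months.

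The size is illustrative: about 1 point for 4–5 relabelled events, at an assumed rate of 6.4–7%. No misclassification rate can be taken from the documents.

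A reader might infer that the bias favours the experimental arm. The documents do not support a direction. Confidence in a negative copeptin result could lower recorded events, while the early cardiologist visit in 7.1 could raise them. The point is a recommended correction to the text; it does not show that the trial's result would be wrong.

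**What to change.** - **14.2.3:** replace the sentence about hard outcomes. State instead that all suspected MACE and bleeding events in both arms are adjudicated by the existing Endpoints Committee, from files with arm and copeptin value removed as far as possible.
- **5.3:** extend the remit to the safety endpoints in 5.2.2, naming 90-day MACE, bleeding and re-hospitalisation for suspected ACS.
- **8.4:** withhold control copeptin results from investigators until database lock.

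The cost is wording plus clerical redaction of event files; the committee already exists. Masking will be imperfect where a file reveals the care pathway, for example an early discharge. The change improves event labelling. It cannot remove bias in open-label decisions to readmit or revascularise, and the protocol should say so as a limitation.
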